This study aims to develop and check the relevance, feasibility, acceptability and safety of adding to standard SUD inpatient treatment a combination of at trauma focused therapy (NET) and treatment for difficulties in emotion regulation (DBT- SUD - Skills). The aim is to measure the presence of trauma and trauma-related difficulties, assesses the pits and falls of the treatments, participation and its safety and potential benefits. Further the study makes it possible investigate the relationship between substance abuse, PTSD, difficulties in emotion regulation, emotional avoidance, shame, guilt and destructive behaviour such as suicide behaviour, self-harm and relapse into substance abuse.

Trial status

We are still open for recruitment, and the last participant is scheduled to be included by the start of May 2024. We plan for the last participant to complete treatment participation by end of October 2024. The data collection for the 3-month and 12-month follow-up will be completed by the end of October 2025.

Future research: If the intervention proves to be relevant, feasible, acceptable and safe, and of potential benefit for the patients, the future aim is to conduct a multicentre Randomized Control Trial (RCT) on the effect of combined NET and DBT-SUD skills integrated into SUD treatment.

Declarations

- *Ethics approval and consent to participate:* The Helsinki Declaration is followed and relevant permissions to the Regional Ethics Committee (REC) and Data Protection Services (DPS) is attained #203 428/2020. Informed consent was obtained from all individual participants included in the study.
- **Consent for publication:** Participants gave written consent for publication of all results not traceable to individual participant.

Availability of data end material: The data can be made available on request.

Competing interests: The authors declare that they have no conflict of interest.

Funding: This study was funded by the Department of Psychiatry, Møre og Romsdal Hospital Trust.

Author contributions: All authors contributed to the study conception and design. [name] and [name] perform material preparation, data collection and analysis. All authors contribute to the design of the study. [name] wrote the first draft of the manuscript and all authors commented on previous versions of the manuscript. All authors read and approved the final manuscript.

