- 2) The percentage of patients that participate in NET and DBT-SUD skills. The dropout rate from the standard treatment, NET and DBT-SUD skills.
- The percentage of DBT-SUD skills sessions participated in, as well as the percentage of completed DBT homework.
- 4) A self-report questionnaire is designed to evaluate the experience of the treatment. Rating how different elements of the treatment are experienced on a 5-point scale. There are also open-ended questions about what is most and least helpful in the treatment.
- 5) The rate of destructive behaviour, such as suicidal behaviour, episodes of drug use and self-harm in the treatment period.

The secondary objective

- Evaluate the relationship between severity of substance abuse, destructive behaviours such
 as suicidal behaviour, self-harm and use of violence with experiences of traumatic events,
 PTSD symptoms severity, difficulties in emotion regulation, emotional avoidance, and
 experience of shame and guilt.
- 2) Evaluate the change from baseline to post-treatment, and at 3 and 12 months follow up, in PTSD symptom severity, depressive symptoms, difficulties in emotion regulation, emotion avoidance, and experience of shame and guilt.
- 3) Compare relapse rates at 3- and 12-months follow-up to previous rates at MBS.

Recruitment of participants:

All patients admitted to the inpatient program at Molde Treatment Center (MBS) from May 2021 to May 2024 will be invited to participate (N approx. = 100). All participants will participate in the standard treatment at MBS. Those who meet the inclusion criteria for further intervention will also be invited to participate in NET and/or DBT-SUD skills. Recruitment and follow-up plan is shown with patient flow chart in fig. 1.

Data collection

We will collect data: Five weeks after admission (T0), four weeks after completion of NET (T1), and at 3 months (T2) and 12 months (T3) follow up after discharge from MBS. An overview of measurements at each data collection point can be seen in table 1. For follow-up, patients will be contacted through telephone, nearest of kin, or social media. Follow-up will be conducted with an outpatient appointment or a home visit. Participation at 3- and 12-month follow will be rewarded with a gift card.

```

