DBT-SUD skills is a group skills training component of Dialectical Behaviour therapy a comprehensive treatment focused on extensive difficulties in emotion regulation (Linehan, 1993). In this project, we will use a combination of the trans-diagnostic skill-training model by Neacsiu (Linehan, 2014; Neacsiu et. al., 2014) with an addition of SUD-specific skills. Every patient participating in the DBT skills training is assigned a DBT-trained therapist.

The DBT-SUD Skills intervention consists of:

- 2-3 sessions with a DBT therapist focusing on treatment orientation – mapping the patients' goals, obstacles, and resources, DBT- hierarchy, and commitment.

- Skills training 20, two-hour sessions twice a week over a period of 10 to 11 weeks. The skills consist of Mindfulness, Distress Tolerance, Interpersonal Effectiveness, Emotion regulation, and SUD-specific skills.
- Chain analysis in case of an episode of substance use or other dangerous destructive behaviour.
- One summary session with a focus on goals reached and troubleshooting.
- Support from DBT skills-oriented staff and environment.

Two DBT therapists lead the group, and each group consists of approx. 6-8 participants.

Patients start NET and DBT- SUD skills training one to two months after admission.

Measurement

Demographics. Basic demographic information from the participants is registered at admission. This includes age, gender, nationality, immigration status, level of education, employment/support status, living situation, marital status, children and custodianship, medical status, and legal status e.g. if the treatment is part of a criminal sentence. As well as questions regarding smoking or non-smoking and substance use cravings.

Substance use

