To assess if adding DBT-SUD skills and NET to standard SUD treatment is relevant, feasible, accepted and safe descriptive statistics will be provided. Descriptive statistics for demographic and psychological factors measured on a continuous scale will be reported in terms of mean or median value with appropriate measure on spread (standard deviation or quartiles) whereas the distribution of categorical factors will be reported in terms of proportions and percentages. Two-sample T-tests will be applied to compare individuals with PTSD/SUB-PTSD vs non-PTSD, abuser vs. non-abuser, participant vs. non- participant, on mean scores on emotions regulation, emotional avoidance, shame, guilt and substance abuse. Analysis of covariance (ANOVA) will be applied to be able to adjust for differences in potential confounders. Non-parametric Kruskal-Wallis tests will be considered if data are skewly distributed. Logistic regression analyses, with calculation of exposure odds ratio, is then relevant for performing adjusted analyses.

Furthermore, Pearson's correlation coefficient and linear or general linear regression analyses is relevant for analysing association between severity of PTSD symptoms on a continuous scale, and degree of emotion regulation, emotional avoidance, shame, guilt, substance use and substance cravings. The non-parametric Spearman rank correlation coefficient is used as an alternative for non-normal data. Logistic regression will be conducted to compare dropout (yes/no; T0, T1) and relapse (yes/no) at 3-months and 12 months follow up (T2, T3) to psychological factors.

To evaluate potential benefits of DBT-SUD skills and NET and symptom reduction at post-treatment (T1), 3 months (T2) and 12 months (T3) follow up, and if the data adhere to assumptions of normal distribution we will conduct one-way repeated measures linear mixed model, adjusting the alpha level to prevent chance capitalization in multiple comparisons we will utilize Holm-Bonferroni corrections. If the data violate the assumption of normal distribution, a generalized mixed model will be conducted. A logistic regression test will be conducted to compare rates of dropout (T0, T1) and relapse at 3-month and 12 months follow up (T2, T3).

Ethics

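### DBT-SUD skills is given in groups of about 6-8, but the model for change names no group term, so its standard errors are too small if members of a group change together

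*Combined protocol and SAP*

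**What the plan says.** **Delivery.** The protocol's section on the intervention states that "DBT-SUD skills is a group skills training component of Dialectical Behaviour therapy". On size and leadership: "Two DBT therapists lead the group, and each group consists of approx. 6-8 participants". On shared exposure: "Skills training 20, two-hour sessions twice a week over a period of 10 to 11 weeks".

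**Who is in a group.** About 100 admissions are expected (Recruitment of participants), and not all of them join a DBT group: "Those who meet the inclusion criteria for further intervention will also be invited to participate in NET and/or DBT-SUD skills". The number expected to enter DBT and the number of groups are not stated. Nor is it stated whether groups are closed or take new members as they run.

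**Analysis.** For symptom change at T1, T2 and T3, which is secondary objective 2, the Statistical analysis section says: "if the data adhere to assumptions of normal distribution we will conduct one-way repeated measures linear mixed model". Holm-Bonferroni correction is applied, and a generalized mixed model is the fallback if normality fails. The section does not list random effects or a covariance structure. Nowhere do the documents mention a DBT group or therapist effect, cluster-robust standard errors, an ICC or a design effect.

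**The concern.** Members of one skills group share their sessions, their fellow members and a period of residence. If some groups go better than others, the changes of their members are correlated, and seven patients from one group carry less information than seven unrelated patients. A one-way repeated measures model has time as its factor and allows for repeated scores on the same patient. It has no place for dependence between patients.

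At stake is the stated precision of the change estimates, which are how the study judges potential benefit. Under Future research, potential benefit is one of the conditions for going on to a multicentre RCT. Intervals that are too narrow would overstate how firmly it has been shown. The Holm-Bonferroni step does not help, because it works on p-values already computed from the standard errors in question.

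**Working it through.** The plan has no sample size calculation, standard deviation, effect size or ICC, so there is no figure of its own to reproduce. The check asks how far the standard error of a mean change could be off.

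**Inputs**
- Group size m: 6-8 from the protocol, midpoint 7.
- Patients: about 100 from the protocol.
- ICC of change within a DBT group: not given. Assumed 0, 0.02, 0.05 and 0.10.
- Test: two-sided 5% per comparison, assumed because no alpha is stated.

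**Formulas**
- Design effect: DE = 1 + (m - 1) × ICC.
- True standard error = naive standard error × √DE.
- True error of a nominal 5% test = 2 × [1 - Φ(1.96/√DE)].

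**All analysed patients in groups of 7**

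| ICC (assumed) | DE = 1 + 6 × ICC | √DE | True error |
|---|---|---|---|
| 0 | 1.00 | 1.00 | 5% |
| 0.02 | 1.12 | 1.06 | 6.4% |
| 0.05 | 1.30 | 1.14 | 8.6% |
| 0.10 | 1.60 | 1.26 | 12% |

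Across m = 6 to 8, DE runs from 1.25 to 1.35 at ICC 0.05 (true error 8.0% to 9.2%) and from 1.50 to 1.70 at ICC 0.10 (11.0% to 13.3%).

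**Simulation check.** With 20,000 replicates of 14 groups of 7, a test of mean change that ignores groups had error 0.051, 0.085 and 0.121 at ICC 0, 0.05 and 0.10. A test on group means stayed between 0.049 and 0.051. With 7 groups of 7 the naive error was 0.048, 0.086 and 0.120.

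**Only part of the sample in groups.** If a share s of the analysed patients is in groups of m and the rest are independent with the same variance, DE = 1 + s × (m - 1) × ICC. With s = 0.5 and m = 7:
- ICC 0.05: 1 + 0.5 × 6 × 0.05 = 1.15.
- ICC 0.10: 1 + 0.5 × 6 × 0.10 = 1.30.

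The excess over 1 is halved.

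**Fewer analysed patients per group.** If dropout or non-consent left 4 of 7 members in the analysis (an illustration, with all analysed patients in DBT), DE would be 1 + 3 × 0.05 = 1.15 and 1 + 3 × 0.10 = 1.30.

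**Number of groups.** If all 100 joined one, 100/8 = 12.5 and 100/6 = 16.7, so about 12-17 at most.

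**The case against.** Several objections have force.

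- **The model is not fully specified.** A reader might infer that the plan expressly treats patients as independent. It does not say so; no random effects are listed. Independence is the natural reading of the named model, but it is inferred from silence.
- **The correlation is unknown.** A reader might also infer that the intervals are in fact too narrow. The documents contain no evidence on this, and at ICC 0 there is no error.
- **The first table is close to a worst case for each ICC.** Patients may receive NET, DBT or both, and the change model is not restricted to DBT patients. The 6-8 counts people in the room. Refusing the study does not affect access to treatment (Ethics), so some members may not be study participants, and others will be lost by T1, T2 or T3.
- **The cluster is not clean.** Everyone lives in one 15-bed therapeutic community with group CBT, so a DBT-group effect would be mixed with calendar cohort, and patients outside DBT are not strictly independent either. If the same two therapists lead every group, which the documents neither state nor exclude, leaders add no variation between groups. T1 is timed from the end of NET, so members of one DBT group need not be assessed together.
- **The consequence is limited.** The analysis is secondary and uncontrolled, the protocol concedes that it cannot measure the direct effect of the intervention, and no stated decision rule depends on these p-values.

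All of this limits size and priority. It does not remove the omission: the treatment is delivered in groups, and the named analysis makes no allowance for that.

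**Conclusion.** The point holds in conditional form and is a cheap improvement. If change is positively correlated within DBT groups, the planned standard errors for change from T0 are too small and the adjusted p-values inherit the fault. On the assumed ICCs of 0 to 0.10, a nominal 5% test would have a true error between 5% and about 12% if every analysed patient sat in a full group of 7, and less with partial DBT uptake or smaller analysed groups. The primary results on relevance, feasibility, acceptability and safety are descriptive and unaffected.

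A further inference should be resisted: that this study would supply the decisive design figure for the later RCT. The within-group correlation is one input among several, the documents do not describe that trial's design, and an estimate from a few groups at one site would be imprecise.

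**What to change.** 1. Record the DBT group of each patient. If groups are open, use the intake block. DBT session attendance is already registered for the primary objective, so membership should be recoverable.
2. State the random effects of the change model. Add DBT group as a random effect on the T1, T2 and T3 scores, absent at T0 and set to zero for patients not in DBT, with Kenward-Roger degrees of freedom. A plain group intercept would not do: an effect that is constant over time cancels out of change from T0.
3. Under the generalized mixed model fallback, use the same random effect, or cluster-robust standard errors by group with a small-sample correction.
4. Report the within-group correlation with its interval, as one imprecise input for the RCT, and note that it may partly reflect calendar cohort in a 15-bed unit.

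**Cost.** One identifier in the data file and one model term. With about 12-17 groups at most, and fewer if uptake is partial, the group variance will be poorly estimated and intervals will widen somewhat. If the variance is estimated as zero, the results are essentially those of the present plan.

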⁴ Regional Center for Violence and Traumatic Stress and St. Olavs Hospital

Introduction

People with SUD are at high risk of developing serious health problems and have high mortality risk (Chesney et al., 2014); this is costly both for the individual and for our society. There are effective evidence-based treatments available for SUD (McGovern & Carroll, 2003), but 40%-70% of patients will relapse into substance abuse within a year of treatment (Roberts et al., 2016). Approximately 36-50% of patients with SUD have comorbid PTSD (Brady et al., 2004). Patients with a combination of SUD and PTSD benefit less from standard SUD treatment. They have stronger drug cravings (Sinha, 2009), more severe substance use (Najavits, 2014), higher risk of SUD treatment dropout and relapse to drug abuse (Ouimette et al., 1998; Tull et al, 2013; Westphal et al., 2017). The lack of benefits from standard SUD treatment could be related to their difficulties in emotion regulation and emotional avoidance (Westphal et al., 2017), as substance abuse can be used to avoid difficult emotions (Linehan, 2013).

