Information about ICD-10 drug diagnoses (F10-19, indicating substance used) and previous SUD inpatient stay, previous inpatient stay (yes/no), onset of substance use, poly drug use (yes/no), and injecting drug use (yes/no) will be obtained from medical records. *Alcohol Use Disorders Identification Test (AUDIT)* is a 10-item screening instrument to assess severity of alcohol consumption, drinking behaviours, and alcohol-related problems. Audit scores range from 0-40 with higher scores indicating greater problems related to alcohol consumptions (Aasland, Amundsen, Bovi, Fauske & Mørland, 1990). In this project, the consumption score (question 1) with cut-of score 3 and over (drinking alcohol 2 -3 times a week) is coded into a dichotomous variable of current alcohol use (yes/no) and sum score used to assess severity of alcohol related problems. At 3 months or 12 months evaluation a cut-off score 3 and over on question 1 is registered as relapse.

Drug Use Disorder Identification Test (DUDIT) is a nine item self-report instrument developed for identification of individuals with drug-related problems. DUDIT scores range from 0-44 with higher scores indicating more drug use and drug related problems (Berman, Palmstierna, Källmén, & Bergman, 2007). In this project, the substance use frequency score (question 1) is used to identify current substance use with cut-off score score 3 and over (using substances 2-3

times a week) will be coded into a dichotomous variable (yes/no). The sum score is used to assess severity of substance related problems. At 3 months or 12 months evaluation a cut-off score 3 and over on question 1 is registered as relapse.

Subjective substance craving the past week is measured on a scale from 0-10, where higher score indicates more substance craving.

Co-occurring psychiatric disorders and symptoms. The presence of current co-occurring psychiatric- and/or personality disorders is obtained from medical records after the standard psychological evaluation at MBS.

Patient Health Questionnaire (PHQ-9) the severity of symptoms of depression is measured with a nine-item self-report providing a 0 to 27 severity score. Higher scores indicate more severe symptoms of depression (Kroenke & Spitzer, 2002).

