Attending study is voluntary and requires an informed consent. Refusing participation in the study will not affect patient's access to treatment. The interventions in the study will not hinder any other well-documented treatment at MBS. The participation is time consuming and demanding for the patient and could temporarily affect the patient's ability to participate in social interaction in the therapeutic community. Answering questions about traumatic experiences can potentially cause discomfort. A therapist and other staff at the clinic will be there to help the patient regulate possible transitory increase in PTSD symptoms. There are number of potential benefits for participants in this project such as access to treatment that can lead to symptom reduction, less suffering, greater quality of life and reduction in relapse into drug abuse. Benefits from participation is supposed to outweighs potential discomfort.

Data Protection: All data will be stored according to established protocols on data protection of More & Romsdal Health trust. The data will be sought to store for up to 5 years after the end of the project. The information will be stored in a de-identified manner. The scoring key will be stored separately in a locked cabinet at MBS, and only two PhD candidates will have access to it. All statistical analysis and use of data collected in this project will be done on a group level.

Strength and limitations

Strength: This is a follow up study with repeated measures in a quite a large sample in naturalistic long-term treatment, making the results generalizable. We have previous data from prior study in the institution on dropout- and relapse rates to use as a comparison.

The results of the study gives relevant information in a population that is often excluded from studies because of drug abuse.

Limitations: With a lack of a randomized control group, one cannot measure the direct effect of the intervention.

SUMMARY

There are high rates of PTSD among patients in with SUD, and a high risk of relapse after treatment. By identifying subgroups of patients with SUD, comorbid PTSD and difficulties in emotion regulation, and develop treatment targeting specifically those areas, one could potentially decrease the suffering of that patient population and decrease relapse to substance abuse.

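### Does the comparison of relapse with earlier rates at the centre need a linked method, a described earlier cohort and a counting rule for untraced patients?

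*Combined protocol and SAP*

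**What the plan says.** Secondary objective 3 is to "Compare relapse rates at 3- and 12-months follow-up to previous rates at MBS". The Strength and limitations section gives the source of those rates: "We have previous data from prior study in the institution on dropout- and relapse rates to use as a comparison". It then concedes that, without a randomised control group, "one cannot measure the direct effect of the intervention".

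The Statistical analysis section uses logistic regression for relapse twice. One sentence looks for predictors within the cohort, among psychological variables (the quote stops one word short of the sentence's end): "Logistic regression will be conducted to compare dropout (yes/no; T0, T1) and relapse (yes/no) at 3-months and 12 months follow up (T2, T3) to psychological". The closing sentence reads "A logistic regression test will be conducted to compare rates of dropout (T0, T1) and relapse at 3-month and 12 months follow up" and names no comparator.

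Under Measurement, the same rule is given once for AUDIT and once for DUDIT: "At 3 months or 12 months evaluation a cut-off score 3 and over on question 1 is registered as relapse". On tracing, the Data collection section says "For follow-up, patients will be contacted through telephone, nearest of kin, or social media", and adds outpatient or home visits and a gift card for attending. The readable text has no rule for patients who are still not reached. The participant flow chart (Fig. 1) is not legible in the copy reviewed.

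**The concern.** Three things look unfinished. First, the closing logistic regression sentence could mean current cohort against earlier cohort, 3 months against 12 months, or participants against non-participants. These are different analyses, and the second has paired data that ordinary logistic regression ignores. Second, nothing is given on the earlier cohort's size, dates, relapse definition or tracing, so a reader cannot tell whether the two rates measure the same thing. Third, relapse status depends on a completed questionnaire at follow-up, and a patient who has relapsed may well be harder to find. A logistic regression run as written would drop untraced patients, and the traced-only rate could then understate relapse.

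At stake is the reading of the study's only external benchmark for relapse. A favourable difference from history could reflect who was found, or how relapse was counted, rather than the treatment.

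**Working it through.** **1. Can the comparison be read from the document?**

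| Element | Where it is given |
|---|---|
| Quantity | Relapse rate (secondary objective 3) |
| Time points | 3 and 12 months after discharge (Data collection) |
| Comparator | Earlier rates at the same centre (secondary objective 3; Strength and limitations) |
| Threshold | Question 1 score of 3 or more (Measurement, AUDIT and DUDIT) |
| Method | Logistic regression (Statistical analysis, closing sentence) |

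The closing sentence pairs dropout with relapse, and the Strength and limitations section offers earlier data on the same pair. The within-cohort use of logistic regression already has its own sentence, and no objective asks for a 3-against-12-month relapse contrast. The historical comparison is therefore the natural reading. A logistic model with a cohort term can be fitted from totals alone (events and numbers), and it carries the earlier cohort's sampling error.

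**2. What could untraced patients do?**

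The plan states no figure to reproduce. Assumed inputs: observed relapse p = 55%, the midpoint of the background range in the Introduction ("40%-70% of patients will relapse into substance abuse within a year of treatment", not a rate from this centre), and untraced share m = 10%, 20% or 30%.

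Bounds run from p(1 − m), if no untraced patient relapsed, to p(1 − m) + m, if all did:

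- m = 10%: 49.5% to 59.5%
- m = 20%: 44% to 64%
- m = 30%: 38.5% to 68.5%

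The width equals m by construction, so the bounds restate the assumed loss and say nothing particular to this trial.

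A milder case takes relapse u = 70% or 80% among the untraced. The shift is m(u − 0.55):

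- m = 10%: 1.5 to 2.5 points
- m = 20%: 3 to 5 points
- m = 30%: 4.5 to 7.5 points

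**3. What happens to the difference from history?**

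Take 40% traced relapse now against 55% before, a difference of −15 points; both rates are assumed. If each cohort loses the same share m, and u is the same in both, the full-cohort difference is

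[p₁(1 − m) + mu] − [p₀(1 − m) + mu] = (1 − m)(p₁ − p₀).

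The value of u cancels. With m = 20% the difference is 0.8 × (−15) = −12 points; with m = 30% it is −10.5. The sign holds.

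If only the current cohort has losses and every untraced patient relapsed, m = 20% gives 0.40 × 0.8 + 0.20 = 52%, a difference of −3. With m = 30% it gives 0.40 × 0.7 + 0.30 = 58%, a difference of +3, and the sign changes. If only the earlier cohort had such losses, its true rate would be above 55% and the gap would widen. The direction therefore depends on facts about the earlier cohort that the document does not give.

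**4. Sampling error for scale**

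Half-width = 1.96 × √[0.55 × 0.45 × (1/n + 1/h)], with n traced now and h in the earlier cohort, both assumed:

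- n = 90, h = 150: 13.0 points
- n = 80, h = 100: 14.6 points
- n = 70, h = 50: 18.1 points

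The values of n come from the planned total of about 100, which the plan attaches to patients invited, so the real n may be smaller and the interval wider.

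**The case for a change.** The strongest case for a change is this. With no control group, history is the only outside yardstick for relapse. The plan lists it as a strength, and the abstract counts relapse among the signs of potential benefit. If the earlier rate were treated as a known constant, a nominal 5% test with 100 current patients would have a true error of 2[1 − Φ(1.96/√(1 + 100/h))], which is about 17% for h = 100 and 26% for h = 50. New wording would need no new patient data, and at the March 2024 revision follow-up was due to run to October 2025.

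Part of this stands. The text is silent on the earlier cohort and on untraced patients. It also does not say whether relapse means AUDIT, DUDIT or either, or whether all participants or only those given NET or DBT-SUD skills are set against history. A report that left these out would be hard to interpret.

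The rest does not carry. The plan never proposes to treat the earlier rate as fixed; it names a regression, which with a cohort term does not do so. The Future research paragraph makes a later randomised trial depend on potential benefit in general and does not mention the historical comparison. It would also be wrong to say that objective 3 has no estimate, since a side-by-side comparison of rates follows directly from the text. If the earlier data use another definition, new wording could only label the comparison descriptive, which is how an uncontrolled comparison would be read in any case.

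**Conclusion.** No change to the plan is needed. The three omissions are correctly observed, but they are detail that a competent analyst supplies when reporting: the earlier cohort's size and definition, the numbers due and traced at each time point, the interval, and the range over untraced patients. No wrong result is shown. Under moderate assumptions (20% untraced, 70-80% of them relapsed) the current rate moves by 3 to 5 points, against a sampling half-width of 13 to 18 points. Larger distortions need one-sided losses with extreme outcomes, and even then the direction against history is unknown.

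Every untraced share, earlier rate and earlier cohort size used here is assumed. The conclusion rests on the comparison being a secondary objective of an uncontrolled feasibility study whose limitations section already rules out a claim of direct effect. It would be different if the historical comparison were a primary outcome or a stated criterion for proceeding to a trial, and it is neither.
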